
Study Objectives
	
Primary Objective (Phase 1b):
 
 1. To determine the safe and recommended Phase 2 dose (RP2D) of APR-246 in combination with azacitidine as determined by dose-limiting toxicities (DLTs) 
Primary Objective (Phase 2):
 
 2. To determine the proportion of patients with TP53 mutant myeloid neoplasms who are in complete remission as measured by the international working group criteria (IWG 2006) 
Secondary Objectives:
 
 3. To determine the duration of response 4. To determine the proportion of patients with TP53 mutant myeloid neoplasms alive at 8 months 5. To determine overall best response rates as measured by the international working group criteria (IWG 2006) 6. To determine if mutant TP53 variant allele frequency (VAF) or p53 protein expression predicts response to APR-246 with azacitidine 7. To determine if p53 protein expression correlates with TP53 VAF 8. To determine if APR-246 with azacitidine treatment leads to mutant TP53 clonal suppression 9. To determine if TP53 clonal suppression correlates with outcomes. 10. To determine if APR-246 treatment upregulates p53 target genes 11. To determine if APR-246 induces reactive oxygen species (ROS) production 12. To determine the rate and time to acute myeloid leukemia (AML) transformation 13. To determine the median overall survival (OS) 14. To determine the median leukemia free survival (LFS) 15. To determine whether recurrent genetic mutations are predictive of response

Study Endpoints
	
Primary
 
 1. Phase 1b: DLTs occurring in the first 2 cycles (8 weeks), as defined below, graded according to the NCI CTCAE, Version 4.03 2. Phase 2: CR rate by IWG 2006 criteria (appendix B) 
Secondary
 
 3. Duration of response defined as the time between achieving response and progression of

	
disease
 
 4. OS at 8 months 5. Proportion of subjects achieving hematological improvement (HI), partial response (PR), complete response (CR), and/or marrow CR (mCR) by the IWG 2006 criteria (appendix B) 6. Proportion of subjects who obtain a response as defined by IWG 2006 criteria with a baseline TP53 VAF $\geq 20\%$ versus $< 20\%$ or high versus low nuclear p53 protein expression 7. Correlation of TP53 VAF with nuclear p53 protein expression as determined by immunohistochemistry (IHC). 8. Proportion of subjects who achieve $\geq 50\%$ reduction in TP53 VAF 9. Progression free survival (PFS) and OS in clonal responders ($\geq 50\%$ reduction in TP53 VAF) versus non-responders 10. Profile expression of genes related to p53-mediated signal transduction before and after APR-246 treatment 11. Profile ROS production before and after APR-246 treatment 12. AML transformation according to World Health Organization (WHO) criteria 13. OS 14. LFS 15. Determine recurrent gene mutations in ASXL1, BCOR, BRAF, CALR, CBL, CEBPA, CSF3R, DNMT3A, ETV6, EZH2, GATA2, GNAS, IDH1, IDH2, JAK2, KIT, KRAS, MPL, NF1, NPM1, NRAS, PDGFRA, PDGFRB, PHF6, PTPN11, RAD21, RUNX1, SETBP1, SF3B1, SMC1A, SMC3, SRSF2, STAG2, STAT3, STAT5b, TET2, TP53, U2AF1, WT1, and ZRSR2 at study entry and serially throughout treatment to assess changes in somatic mutation landscape

Eligibility Criteria
	
Inclusion Criteria:
 
 1. Patient has signed the Informed Consent (ICF) and is able to comply with protocol requirements. 2. Patient has adequate organ function as defined by the following laboratory values: 
 a. Serum creatinine $\leq 2 \times$ upper limit of normal (ULN) b. Total serum bilirubin $< 1.5 \times$ ULN or total bilirubin $\leq 3.0 \times$ ULN with direct bilirubin within normal range in patients with well documented Gilbert's Syndrome or hemolysis or who required regular blood transfusions c. Alanine aminotransferase (ALT) and aspartate aminotransferase (AST) $< 2.5 \times$ ULN 3. Age ≥ 18 years at the time of signing the informed consent form 4. Documented diagnosis of myelodysplastic syndrome (MDS), MDS/ myeloproliferative neoplasm (MPN), chronic myelomonocytic leukemia (CMML) by WHO criteria or AML with 20-30% myeloblasts (refractory anemia with excess blasts in transformation

(RAEB-T) by French-American-British (FAB) criteria).

5. Documentation of a *TP53* gene mutation by next-generation sequencing (NGS) based on central or local evaluation.
6. Revised International Prognostic Scoring System (IPSS-R) criteria for Intermediate, High-risk or Very High-risk.
7. An Eastern Cooperative Oncology Group (ECOG) performance status score of 0, 1, or 2 is required.
8. If of childbearing potential, negative pre-treatment urine or serum pregnancy test.
9. If of childbearing potential (males and females), willing to use an effective form of contraception such as latex condom, hormonal birth control, intrauterine device or double barrier method during chemotherapy treatment and for at least six months thereafter.

Exclusion Criteria:

1. Patient has a known history of HIV or active hepatitis B or active hepatitis C infection (testing not mandatory).
2. Patient has any of the following cardiac abnormalities (as determined by treating MD):
 - a. symptomatic congestive heart failure
 - b. myocardial infarction \leq 6 months prior to enrollment
 - c. unstable angina pectoris
 - d. serious uncontrolled cardiac arrhythmia
 - e. QTc \geq 470 msec
3. Concomitant malignancies or previous malignancies with less than a 1-year disease free interval at the time of signing consent. Patients with adequately resected basal or squamous cell carcinoma of the skin, or adequately resected carcinoma in situ (e.g. cervix) may enroll irrespective of the time of diagnosis.
4. Prior exposure to azacitidine, decitabine or investigational hypomethylating agent
5. Use of cytotoxic chemotherapeutic agents, or experimental agents (agents that are not commercially available) for the treatment of MDS, MDS/MPN, CMML or AML within 14 days of the first day of study drug treatment.
6. No concurrent use of erythroid stimulating agents, G-CSF, GM-CSF is allowed during study except in cases of febrile neutropenia where G-CSF can be used for short term. Growth factors must be stopped 14 days prior to study.
7. Patients with history of allogeneic stem cell transplantation.
8. Pregnant women are excluded from this study because APR-246 has not been studied in pregnant subjects. Because there is an unknown but potential risk for adverse events in nursing infants secondary to treatment of the mother with APR-246, breastfeeding should be discontinued if the mother is treated with APR-246.

Baseline Assessment (within 4 weeks of starting treatment)
	
1. Medical history including:
 
 a. disease characteristics such as WHO subtype, IPSS/R-IPSS score, prior treatments b. ECOG performance status c. Concurrent medication review 
2. Routine physical examination
 
3. EKG
 
4. Bone marrow examination, including cytomorphology, cytogenetic assessment, and flow cytometry analysis
 
5. Documentation of a TP53 gene mutation by NGS based on central or local evaluation
 
6. Laboratory assessments:
 
 • CBC with differential (including platelet count) • Clinical chemistries including BUN, creatinine, sodium, potassium, alkaline phosphatase, ALT, AST, total bilirubin and albumin • Urine or serum pregnancy test for females of childbearing potential will be performed between Screening and first day of treatment on study, prior to first dose of study medication. 
7. Review and record any red blood cell and platelet transfusions for the prior 8 weeks.


Treatment plan
	
Treatment will be administered on an outpatient basis. Reported adverse events and potential risks are described in Section 11. Appropriate dose modifications for APR-246 are described in Section 10. No investigational or commercial agents or therapies other than those described below may be administered with the intent to treat the patient's disease. APR-246 will be supplied by Aprea.
 
APR-246 will be administered as a 6 hour intravenous infusion daily on days 1-4 for each 28 day cycle. Azacitidine will be given at the standard dose of 75mg/m² over 7 days (7 consecutive days, 4-10; or 2+5 (i.e., days 4-5 and 8-12) as a subcutaneous injection or intravenous infusion. A maximum of 51 subjects will be treated. See study calendar for assessment on study.

Definition of DLT
	
Patients will be evaluated for DLTs during the lead-in phase and first cycle of combination therapy, i.e., 6 weeks for purpose of deciding the dose for next cohort (see Table 1) but DLTs will continue to be evaluated and reported through all cycles on study. DLT is defined as follows based on the CTCAE v 4.03:
 
 -Treatment related non-hematological CTCAE grade 3-4 toxicity that lead to dose modification or withdrawal. -Absolute neutrophil count (ANC) not recovering to >500/μL by day 42 of a cycle in the absence of active leukemia/myelodysplasia will be considered a DLT. -Grade 3 metabolic/electrolyte abnormalities that are not clinically significant, and are adequately controlled within 72 hours are not to be considered DLT. -Grade 3 nausea/vomiting/diarrhea or CNS toxicity that does not resolve within 28 days despite

	treatment interruption and maximum medical therapy will be considered a DLT.
Dose delay / modifications	Dose delays/modifications are allowed as described in section 10.
Duration of Therapy	
Subjects will be treated for a total of 6 cycles. For subjects responding or who have stable disease following cycle 6, treatment may continue until one of the following criteria applies:
 
 • Inter-current illness that prevents further administration of treatment, • Unacceptable adverse event(s), • Patient decides to withdraw from the study, or • General or specific changes in the patient's condition render the patient unacceptable for further treatment in the judgment of the investigator. • Evidence of disease progression by the IWG 2006 criteria (see Appendix B, not applicable at bone marrow evaluation at day -10 of lead in phase). 
Subjects who wish not to continue treatment at time of disease assessment at end of cycle 6 will complete their end of treatment visit upon completion of cycle 6.

Duration of Follow-Up	
Subjects will be followed as per calendar on treatment for 6 cycles (Figure 2). After 6 cycles, subjects who continue on study will be followed monthly. Off treatment data on AML transformation and overall survival will be updated every 6 months or until death, whichever occurs first. Subjects removed from the study for unacceptable adverse events will be followed until resolution or stabilization of the adverse event.
 
Criteria for Removal from Study
 
Study drug treatment can continue for subjects receiving clinical benefit, unless: one or more withdrawal criteria are met, or at the subject's discretion, or if the study is terminated.
 
1. Subject Completion
 
A subject will be considered to have completed the study if the subject meets at least 1 of the following criteria:
 
 - The subject has progressive disease. - The subject died during the study. - The subject experienced a treatment related AE that led to withdrawal from the study. - The subject starts new treatment for their underlying disease (MDS/CMML/AML). 
2. Subject Withdrawal from Study:
 
A subject may voluntarily withdraw from study medication or withdraw consent from the study at any time. The investigator may also, at his or her discretion, discontinue a subject from participating in the study at any time. The investigator and/or designated staff will record the date and the reason for subject withdrawal from the study.
 
3. Subject Withdrawal from Study Medication:
 
If the subject is permanently withdrawn from treatment with study medication, but does not withdraw consent, the investigator must make every effort to have the subject complete all

	
withdrawal assessments at the time of withdrawal, and complete all scheduled follow-up visits.
 
Treatment with study medication must be discontinued if (Withdrawal Criteria):
 
Evidence of Disease progression according to IWG 2006 criteria (see Appendix B, not applicable at bone marrow evaluation at day -10 of lead in phase).
 
A subject becomes pregnant.
 
A subject is significantly non-compliant with the requirements of the protocol;
 
A subject has an adverse experience that would, in the investigator's judgment, make continued participation in the study an unacceptable risk
 
A subject withdraws consent

Follow up on study	See calendar Section 13

Statistics

Study Design:

[figure not shown]
This study will be a multi-institution, open-label, phase Ib/II clinical trial conducted in 2 parts: a Phase 1b part followed by a Simon’s two-stage Phase 2 design. The study will assess the safety and efficacy of APR-246 in combination with azacitidine for the treatment of *TP53* mutant myeloid neoplasms. All patients will have pre-screening NGS on peripheral blood (PB) or bone marrow (BM) samples to determine *TP53* mutational status and therefore eligibility to participate in this study. A PB sample will be obtained prior to treatment for NGS by the central laboratory to evaluate baseline *TP53* VAF and for serial analysis.

Evaluable: Patients will be evaluable for inclusion in the Phase 1b and Phase 2 portions of the study if they receive at least one dose of protocol therapy.

Phase 1b Part:

The initial Phase 1b part will evaluate APR-246 administered with azacitidine (see Figure 1). Cohorts of at least 3 evaluable patients will be enrolled using a modified 3 + 3 design.

Figure 1

Patients will receive intravenous infusions of APR-246 as a lead-in phase on days -14 to -11 starting at Dose Level 1 (see Table 1) prior to starting cycle #1 of combination therapy with azacitidine (see Figure 1). Combination therapy will consist of APR-246 on days 1-4 and azacitidine on days 4-10 (or days 4-5 and 8-12) of a 28 day cycle. Patients will be followed for at least 6 weeks (lead in phase + cycle 1) before the safety of each cohort can be fully assessed and decisions made for dose escalation in the next cohort. The MTD is defined as the dose level below which DLT is manifested in $\geq 33\%$ of the patients or at dose level 3 if DLT is manifested in $< 33\%$ of the patients.

Table 1. Dose Levels for Treatment Part 1: APR-246+Azacitidine

Dose Level	APR-246 (mg/kg lean body weight (LBW))	Azacitidine (mg/m ²)
1 (Starting dose)	50	75
2	75	75
3	100	75

Phase 1b, patients (n = 6 to approximately 18) will receive APR-246 in combination with azacitidine. Cohorts of at least 3 evaluable patients will be enrolled using a modified 3+3 design. If no DLT is observed in a cohort, the subsequent patient group will be enrolled at the next planned dose level. If a DLT is observed in 1 of 3 patients in a cohort at any dose level, then up to 3 additional patients will be enrolled at that dose level. If only 1 DLT occurs in the 6 patients treated at that dose level, the subsequent patient group will be enrolled at the next planned dose level. If 2 of 6 patients in a cohort have a DLT, dose escalation ceases and the MTD is the previous dose level. If only 3 patients were treated at the MTD, an additional 3 patients will be included in the cohort and if only 0 or 1 DLT occur in the 6 patients treated at that dose level, the MTD will be defined and we will proceed to Phase 2.

[figure not shown]
Phase 2: Simon’s two-stage minimax design:

Following completion of the Dose Finding Phase, we will conduct a dose expansion, whereby patients will be treated with APR-246 administered at the MTD with azacitidine on a 28 day cycle utilizing the same dosing schedule as in Phase 1b with the exception of no lead in phase (i.e. patients will start at day 1 of combination therapy with APR-246 on days 1-4 and azacitidine on days 4-10 (or days 4-5 and 8-12) of a 28 day cycle, see Figure 1). If dose level 3 (i.e. 100mg/kg LBW) is the RP2D based on the phase 1b part of the trial, the dosing will be changed to an equivalent fixed dose regimen of 4500mg/patient (see below). All patients who complete at least one treatment cycle of APR-246 and azacitidine and who have at least one post-treatment clinical response assessment will be considered eligible for the efficacy-evaluable population and will be summarized for all efficacy variables. Patients who fail to complete one treatment cycle will also be considered efficacy-evaluable if they show clear evidence of clinically significant disease progression. Patients who are not efficacy-evaluable will be replaced. A Simon’s two-stage minimax design will be applied, as follows:

Stage 1: Enroll a total of 24 evaluable patients at the MTD (including patients who were enrolled during the Phase 1 part of the study). If less than 6 of 24 patients achieve CR, then the study will be terminated early with the conclusion that the regimen does not warrant further investigation. If 6 or more patients achieve CR, then enrollment will be permitted to continue to Stage 2.

Stage 2: Enroll 21 more evaluable patients for a total of 45. If less than 14 of 45 patients achieve CR, then there is insufficient evidence to support continued study of this treatment. If at least 14 of 45 patients achieve CR, then there is sufficient evidence to support further study of APR-246 in combination with azacitidine in Phase 3. Up to 39 additional evaluable patients will be treated at the level of the MTD in the Phase 2 portion of the trial. The maximum total accrual is 51 patients. Disease assessments will occur following 3 cycles of therapy (Figure 3).

Figure 3. Phase 2 Schema

This rule has the following operating characteristics: 90% power, with alpha=0.05 under the null hypothesis that the proportion of patients achieving CR is $\leq 20\%$ versus the alternative hypothesis that it is $\geq 40\%$. This design has a probability of early termination equal to 0.66 if the true CR rate is 20%.

Number of Patients Planned:

The number of patients enrolled will depend on the number of dose levels evaluated before reaching DLT. Three to 6 evaluable patients will be entered per dose level. It is anticipated that up to 18 evaluable patients can be treated in the Phase 1b portion of the study. Up to 39 additional evaluable patients will be treated at the level of the MTD in the Phase 2 portion of the trial. The maximum total accrual is 51 patients.

Analyses to address study objectives

To address the primary objective for Phase 1b, we will apply the 3+3 design above.

To address the primary objective for Phase 2, we will apply the Simon's two-stage minimax design above.

Analysis of the following secondary endpoints will be of exploratory nature:

Duration of response defined as the time between achieving response and progression of disease.

OS at 8 months

Proportion of subjects achieving hematological improvement (HI), partial response, complete response (CR), and/or marrow CR (mCR) by the IWG 2006 criteria (see appendix B)

Proportion of subjects who obtain a response as defined by IWG 2006 criteria with a baseline *TP53* VAF $\geq 20\%$ versus $< 20\%$ or high versus low nuclear p53 protein expression

Correlation of *TP53* VAF with nuclear p53 protein expression as determined by IHC

Proportion of subjects who achieve $\geq 50\%$ reduction in *TP53* VAF

Progression free survival (PFS) and OS in clonal responders ($\geq 50\%$ reduction in *TP53* VAF) versus non-responders

Profile expression of genes related to p53-mediated signal transduction before and after APR-246 treatment

Profile ROS production before and after APR-246 treatment

AML transformation according to World Health Organization (WHO) criteria

OS

LFS

Determine recurrent gene mutations in *ASXL1*, *BCOR*, *BRAF*, *CALR*, *CBL*, *CEBPA*, *CSF3R*, *DNMT3A*, *ETV6*, *EZH2*, *GATA2*, *GNAS*, *IDH1*, *IDH2*, *JAK2*, *KIT*, *KRAS*, *MPL*, *NF1*, *NPM1*, *NRAS*, *PDGFRA*, *PDGFRB*, *PHF6*, *PTPN11*, *RAD21*, *RUNX1*, *SETBP1*, *SF3B1*, *SMC1A*, *SMC3*, *SRSF2*, *STAG2*, *STAT3*, *STAT5b*, *TET2*, *TP53*, *U2AF1*, *WT1*, and *ZRSR2* at study entry and serially throughout treatment to assess changes in somatic mutation landscape

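### The stated maximum of 51 patients cannot guarantee the 45 evaluable MTD patients that Stage 2 needs; the plan's own rules reach 57

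*Combined protocol and SAP*

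**What the plan says.** The ceiling appears four times. The Treatment plan row of the synopsis says "A maximum of 51 subjects will be treated". The sentence "The maximum total accrual is 51 patients" stands in the synopsis under Stage 2, again in the synopsis under Number of Patients Planned, and in section 6 under Stage 2.

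The other headcounts are:

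- Per dose level (synopsis, Number of Patients Planned): "Three to 6 evaluable patients will be entered per dose level". There are three levels. After one DLT in three patients at any level, "then up to 3 additional patients will be enrolled at that dose level" (synopsis and section 6, Phase 1b). One DLT in six still permits escalation. An MTD cohort of three is filled to six.
- Phase 1b total (Number of Patients Planned): "It is anticipated that up to 18 evaluable patients can be treated in the Phase 1b portion of the study".
- Phase 2: "Up to 39 additional evaluable patients will be treated at the level of the MTD in the Phase 2 portion of the trial".
- Stage 1 takes 24 evaluable patients at the MTD, including those from Phase 1b: "If less than 6 of 24 patients achieve CR, then the study will be terminated early". Stage 2: "Enroll 21 more evaluable patients for a total of 45".

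Patients who are not efficacy-evaluable are to be replaced; no number is given. Section 15.1 repeats the 24, the 45 and the 39 but not the ceiling of 51.

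**The concern.** The 39 is 45 minus the 6 Phase 1b patients at the MTD. Adding it to a Phase 1b of up to 18 gives 57, not 51. The figure of 51 corresponds to a Phase 1b of 12 (3, 3 and 6 patients), although the same paragraph allows 18.

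Nothing in the plan says whether the 45 or the 51 gives way when they conflict. The conflict would surface only after Stage 1 has passed, in an open-label trial with CR results known. The team would then have to exceed a stated maximum or stop short of the size to which the final cut-off and the stated power belong.

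**Working it through.** **1. The plan's Simon figures.** Inputs are from the synopsis and section 15.1: n1 = 24, continue with at least 6 CRs; n = 45, success with at least 14; null 20%, alternative 40%.

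P(success | p) = Σ over x = 6 to 24 of Bin(x; 24, p) × P[Bin(n − 24, p) ≥ 14 − x].

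- Early termination at 20%: 0.656 (stated 0.66)
- Type I error at 20%: 0.0483 (stated limit 0.05)
- Power at 40%: 0.9001 (stated 90%)

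All three reproduce, so 45 is the size the design needs.

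**2. The headcount.** Total evaluable = patients off the MTD + 45.

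| Phase 1b cohorts, MTD at level 3 | Off MTD | Total needed | MTD places left under 51 |
|---|---|---|---|
| 3 / 3 / 6 | 6 | 51 | 45 |
| 6 / 3 / 6 or 3 / 6 / 6 | 9 | 54 | 42 |
| 6 / 6 / 6 | 12 | 57 | 39 |

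One expanded lower cohort is enough to break the ceiling here. The 57 also arises with the MTD at level 2 when level 3 stops after six patients. Conversely, if the MTD is level 1 and level 2 stops after three, 48 is enough. Stage 1 alone always fits: 24 + 12 = 36.

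**3. Operating characteristics if 51 is enforced.** Same formula with smaller n:

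| n at MTD | Type I error, ≥14 | Power, ≥14 | Type I error, ≥13 | Power, ≥13 |
|---|---|---|---|---|
| 44 | 0.0411 | 0.884 | above 0.05 | – |
| 43 | 0.0346 | 0.865 | above 0.05 | – |
| 42 | 0.0287 | 0.842 | 0.0579 | – |
| 41 | 0.0236 | 0.816 | 0.0494 | 0.883 |
| 40 | 0.0191 | 0.784 | 0.0415 | 0.862 |
| 39 | 0.0152 | 0.749 | 0.0345 | 0.838 |

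Sizes 40, 41, 43 and 44 occur only if an expansion is stopped at the second DLT, which the wording of up to three additional patients allows. Cohorts filled to six give 42 or 39.

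**4. How often the ceiling would bind.** The documents give no DLT rate for this combination, so the rates below are assumptions. Section 2.5.1 reports no DLTs at 67.5 mg/kg, which section 2.5.2 equates with 100 mg/kg lean body mass. That is a small sample without azacitidine: it makes low rates plausible but fixes none. All 3+3 paths were enumerated. Two further assumptions were made: two or more DLTs in the first three patients stop escalation (the plan states no action for this), and an MTD cohort that fails when filled to six moves the MTD down one level.

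Stage 1 passes with probability 0.344 at a 20% CR rate and 0.960 at 40%. Multiplying by the chance of more than 6 off the MTD, given that an MTD is found:

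| Assumed DLT rates, levels 1/2/3 | More than 6 off MTD | Exactly 12 off | Binds, CR 20% | Binds, CR 40% | Mean power under 51, ≥14 |
|---|---|---|---|---|---|
| 1/2/3% | 9% | 0.2% | 3% | 9% | 0.895 |
| 2/5/8% | 21% | 0.9% | 7% | 20% | 0.887 |
| 5/10/15% | 36% | 3.7% | 12% | 35% | 0.876 |
| 10/15/20% | 43% | 7.1% | 15% | 41% | 0.869 |
| 5/15/35% | 45% | 5.9% | 15% | 43% | 0.869 |

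The last column and the column for exactly 12 take expanded cohorts as filled to six. Stopping at the second DLT gives mean powers of 0.888, 0.879, 0.873 and 0.877 in the last four rows. When the ceiling binds, 42 is the most common size: 83 to 96% of cases with filled cohorts and 48 to 82% with early stopping, over the last four rows.

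**The case against.** The conflict is conditional. The Phase 1b figure is only anticipated or approximate, the limits need not all be reached together, and 51 is exact when no lower cohort is expanded. It needs more than 6 patients off the MTD and a pass at Stage 1. The off-MTD count is known when Phase 1b ends, so the ceiling could be amended before it does harm. Section 15, which holds the statistical rules, carries no ceiling. The average power loss is small, the 74.9% needs all 12 off-MTD places used, and the binding percentages depend on assumed DLT rates.

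Most of this is right and limits the size of the problem. It does not remove it. The words anticipated and approximately qualify the 18, not the expansion rule that produces it, and the plan calls 51 a maximum. A later amendment is possible, but nothing in the plan provides for one or says which number yields. The 57 depends on none of the assumed rates or the added stopping assumptions.

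**Conclusion.** The concern holds. As a maximum, 51 is wrong by up to 6 evaluable patients (57 against 51), and replacements would widen the gap. This rests only on the plan's cohort sizes, three dose levels and the 45 at the MTD. It should be fixed, but it does not undermine the design: the Simon boundaries are correct, Stage 1 is unaffected and type I error stays below 0.05 if at least 14 CRs are still required.

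If 51 were enforced, power on an affected path would be between 74.9% and 88.4%, most often 84.2% (42 patients). Averaged over paths it would be about 87 to 89% in four of the five assumed scenarios and 89.5% in the lowest. The chance that the ceiling binds is 3 to 15% at a 20% CR rate and 9 to 43% at 40%; these ranges show the assumed DLT rates, not evidence about this trial.

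**What to change.** Preferred: in all four statements, give the maximum as 57 evaluable patients (up to 12 off the MTD plus 45 at the MTD) and say that replacements come on top. If a ceiling on patients treated is also wanted, add an explicit replacement allowance. The cost is a short amendment and a stated ceiling up to 6 higher plus replacements; the Simon boundaries and the endpoint do not change.

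Alternative: keep 51 as a hard ceiling and state the rule for a shortened Stage 2 in advance. That means at least 14 CRs with 42, 43 or 44 patients (power 84.2, 86.5 or 88.4%) and at least 13 with 39, 40 or 41 (power 83.8, 86.2 or 88.3%), in place of the single claim of 90% at 14 of 45. Replacements would have to fit within 51 too. The cost is lower stated power and a longer decision rule. Under either option, section 15.1 should carry the same figure as the synopsis and section 6.
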